Thus, it is also a highly selective inhibitor of aromatase. The high potency and selectivity of letrozole explains its favorable pharmacological profile and high therapeutic index. In postmenopausal patients with advanced breast cancer, daily doses of 0.1 to 5 mg letrozole suppressed plasma levels of estradiol, estrone and estrone sulfate by 75-95% from baseline.¹⁴

- 2.1.2.2 Clinical Information: A Phase III global, multicenter, randomized clinical trial evaluated letrozole (2.5 mg/day) as a first-line hormonal therapy as compared to the present standard of treatment tamoxifen (20 mg/day).8 This trial accrued 907 postmenopausal women with ER and/or PR positive or unknown receptor breast cancer and locally advanced disease, metastatic disease, or loco-regional recurrence not amenable to treatment by surgery or radiotherapy. Patients received treatment until disease progression or discontinuation for any other reason. The primary endpoint was time to progression (TTP). Letrozole was superior to tamoxifen and reduced the risk of progression by 28% (hazard ratio 0.72, P < .0001). The median TTP was prolonged by 57%: 6.0 months for tamoxifen vs. 9.4 months for letrozole. The secondary endpoints included overall tumor response rate, clinical benefit, and time to treatment failure. Overall tumor response rate (complete and partial response) was significantly higher with letrozole (32% vs. 21%, P = .0002), irrespective of dominant site of disease. Clinical benefit (complete response, partial response or stabilization of disease) lasting at least 24 weeks was 50% for letrozole vs. 38% for tamoxifen (P = .0004). Time to treatment failure was significantly better for letrozole compared to tamoxifen (9.0 months vs. 5.7 months respectively, P = .0001.) The median overall survival was slightly prolonged for letrozole vs. tamoxifen (34 months vs. 30 months, respectively). This difference is not significant. However, the study design included a crossover to the other treatment arm at the discretion of the investigator. An analysis was done in the patients who did not crossover, which demonstrated a 15-month survival advantage in the letrozole treatment group. 15 The data cutoff for this analysis was September 2001 when median follow-up was 32 months with a maximum observation period of 57 months. Tolerability was similar in both arms of the trial, with 2% of patients on letrozole and 3% of patients on tamoxifen discontinuing therapy due to adverse events.

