2.1.3.3 Summary: Although studies demonstrate limited activity of sorafenib as a single-agent in heavily pre-treated metastatic breast cancer populations, there is potential for efficacy in combining sorafenib with other agents, such as chemotherapy, hormone therapy and other targeted drugs. There are several ongoing trials being conducted with sorafenib in patients with metastatic breast cancer. This includes a phase II trial of sorafenib and anastrozole in previously treated patients with hormone receptor-positive disease, a randomized phase II trial of paclitaxel with or without sorafenib as first-line therapy in locally recurrent or metastatic breast cancer, and a double-blind, randomized

phase II trial of sorafenib versus placebo in combination with chemotherapy after progression on bevacizumab.

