16.1 Primary and Secondary Hypotheses

The study will require a short run-in phase I portion to determine the recommended phase II dose. The primary objective of the single arm single-stage phase II portion of the study is to determine the clinical benefit rate (proportion of patients who achieve a complete response, partial response, or stable disease ≥ 6 months) of letrozole and sorafenib as first-line therapy in postmenopausal women with hormone receptor-positive locally advanced or metastatic breast cancer. The secondary objectives are to determine the safety and tolerability of sorafenib in combination with letrozole and evaluate time to progression and overall survival.

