16.2 Sample Size Justification

A historical study showed that single-agent letrozole in the first-line treatment of patients with hormone receptor-positive metastatic breast cancer had a clinical benefit rate of 50% compared to tamoxifen. The combination therapy of letrozole and sorafenib will not be considered of further interest if the true clinical benefit rate is less than or equal to 50%. We assume that this study will target a clinical benefit rate of 67% for identifying the combination therapy as active and worthy of further investigation. With these settings, the null hypothesis is that the clinical benefit rate of the combination therapy is less than or equal to 50%, and the alternative hypothesis is that the clinical benefit rate of 67% or more is of considerable interest. For the phase II part of the study, the sample size was calculated according to a single-stage design. The study will accrue a total of 58 patients, and the combination therapy will be accepted if there are at least 35 responders out of 58 patients. The design will have a 4.3% (< 5%) type-I error (false positive) rate and a power of 82.7% (> 80%) (i.e., 17.3% type-II error or false negative rate). The total number of evaluable patients to be accrued to this study is not expected to exceed 64 patients.

Phase I/II Trial of Letrozole (and Sorafenib as First-Line Therapy in Postmenopausal Women with Hormone Receptor-Positive Locally Advanced or Metastatic Breast Cancer PI:

The patients accrued in the Phase I dose escalation will be included in the Phase II portion if they receive the same dose. Evaluable patients for the phase I portion are defined as study-eligible patients who have received at least one cycle of treatment. Evaluable patients for the phase II portion are those who have received at least two cycles of treatment.

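### Optional improvement: the single-stage phase II has no futility look, and one non-binding look at 29 women would cost under one point of power

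*Combined protocol and SAP*

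**What the plan says.** Section 16.1 describes a "single arm single-stage phase II portion of the study". Section 16.2 confirms that "the sample size was calculated according to a single-stage design". It states that "The study will accrue a total of 58 patients", with success declared at 35 or more responders, a type I error of 4.3% and a power of 82.7%. The "null hypothesis is that the clinical benefit rate of the combination therapy is less than or equal to 50" percent, and "this study will target a clinical benefit rate of 67" percent.

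The null value is the letrozole result of the phase III trial summarised in section 2.1.2.2, where clinical benefit "lasting at least 24 weeks was 50% for letrozole". Section 16.2 adds that the combination is of no further interest at 50% or less.

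Section 16.4 lists only final summaries. Sections 14, 15.8 and 15.9 deal with audits, data verification and compliance. The rules in section 7.4.1 act on dose-limiting toxicity in cycle 1, and the off-study criteria in section 10 act on one patient at a time. None of them responds to the observed benefit rate.

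On sorafenib, section 2.1.3.3 says that "studies demonstrate limited activity of sorafenib as a single-agent in heavily pre-treated metastatic breast cancer populations". The same sentence goes on to see potential for efficacy in combination with other agents.

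**The concern.** The plan names a benefit rate at which it would lose interest in the combination, but gives itself no chance to act on that rate before the last woman is enrolled. At a true rate of 50% every woman would be taking sorafenib, with its side effects, for no gain over letrozole. Section 17.5 concedes that superiority over letrozole alone is not established, so this outcome has to be planned for. The stated power of 82.7% is above the 80% floor in section 16.2, which leaves some room to pay for a look.

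**Working it through.** **Inputs (section 16.2).** n = 58, p0 = 0.50, p1 = 0.67, printed rule 35 or more, stated type I error 4.3% and power 82.7%.

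**Step 1: the plan's own figures.** Exact binomial, P(X ≥ r) with X ~ Bin(58, p):

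| Cut-off r | Type I error (p = 0.50) | Power (p = 0.67) |
|---|---|---|
| 35 (printed) | 7.40% | 88.71% |
| 36 | 4.35% | 82.65% |

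The stated 4.3% and 82.7% belong to 36 or more. The printed cut-off does not reproduce them, so both are carried forward.

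**Step 2: the look.** Stop if X1 ≤ 14 among the first 29; otherwise continue to 58 and apply the same final cut-off. The stopping probability is P(X1 ≤ 14), X1 ~ Bin(29, p):

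| True rate | Probability of stopping |
|---|---|
| 45% | 70.7% |
| 50% | 50.0% |
| 60% | 13.6% |
| 67% | 2.8% |

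**Step 3: effect on error rates.** P(success) = Σ over x from 15 to 29 of P(X1 = x) · P(X2 ≥ r − x), with X2 ~ Bin(29, p):

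| Cut-off r | Type I error | Power | Power lost |
|---|---|---|---|
| 36 | 4.35% → 4.27% | 82.65% → 82.19% | 0.45 points |
| 35 | 7.40% → 7.16% | 88.71% → 87.94% | 0.78 points |

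If the look is overruled, the error rates return at most to those of the single-stage rule.

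**Step 4: is 14 a sensible boundary?** With 14 of 29, reaching 36 needs 22 of the remaining 29. That has probability 0.4% at a true rate of 50% and 21% at 67%. With cut-off 36, a boundary of 13 stops 35.6% of the time at the null and costs 0.10 points of power; a boundary of 15 stops 64.5% of the time and costs 1.64 points.

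**Step 5: women spared by a stop.** If accrual continues during the wait, a stop spares 29 − (accrual per month × lag in months), or none if that is negative. The documents give no accrual rate; the rates below are assumptions. The lag is also assumed: 6 months if status is known at six months, or about 8.3 months if it waits for the week-36 scan (252 days ÷ 30.44), since section 6 schedules scans every 12 weeks.

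| Accrual per month | Lag 6 months | Lag 8.3 months |
|---|---|---|
| 1 | 29 − 6 = 23 | 29 − 8.3 ≈ 21 |
| 3 | 29 − 18 = 11 | 29 − 24.9 ≈ 4 |
| 5 | none (29 − 30 < 0) | none |

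These numbers are conditional on a stop. At a true rate of 50% the expected saving is half of each.

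**Step 6: precision after a stop.** The 95% half-width near 50% is 1.96·√(0.25/n): ±18 points at n = 29 and ±13 at n = 58.

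**Step 7: who is in the 29.** Section 16.2 makes women evaluable for phase II only after two cycles. Suppose a share d of women is dropped and all of them are failures (assumption). A true rate of 50% then appears as 0.50/(1 − d). For d = 5% this is 52.6%, and the stopping probability falls from 50% to 39%. For d = 10% it is 55.6%, and the probability falls to 27%.

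**The case against.** A single-stage design is declared consistently in sections 16.1 and 16.2 and is a legitimate choice. That stands: nothing here is a mistake in the plan, and the point is optional advice.

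The gain may be small or nil. That stands too. The benefit endpoint takes about six months or longer to read, the accrual rate is unknown, and with fast accrual a stop would spare nobody.

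The cost is more than power. The primary objective in section 1.1.2 is to determine the benefit rate, and closing near 29 women widens its interval. It also leaves less information on time to progression, survival, safety and the biological endpoints. At a true rate of 60%, which is above the null, the look would still suggest closing 13.6% of the time. These costs are real and should be stated beside the rule.

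A reader might infer that the plan exposes women to a toxic drug already shown not to work in breast cancer. The documents do not support that. The limited single-agent activity was seen in heavily pre-treated women, section 2.1.3.2 describes the main side effects as mild to moderate and manageable, and every woman on this trial receives letrozole. A reader might also infer that power with the look is simply 82.2%. That is true only with a final cut-off of 36; with the printed 35 it is 87.9%, with a type I error of 7.2%.

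**Conclusion.** The phase II part has no efficacy or futility look, and one could be added cheaply. Stopping at 14 or fewer of 29 gives an even chance of early closure when the true rate is 50%, and a 2.8% chance when it is 67%. It costs 0.5 points of power at cut-off 36 or 0.8 points at cut-off 35, stays above 80% in both cases, and does not raise the type I error.

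These figures assume that the 29 women are the first of the same 58 counted at the end, under one counting rule. The even chance of closure falls if early failures are left out of the 29. The practical benefit cannot be fixed from the documents because it depends on accrual and on when clinical-benefit status is taken as known. This is an improvement to consider, not a defect that must be corrected.

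**What to change.** 1. In section 16.2, first reconcile the cut-off with the stated error rates: 4.3% and 82.7% go with 36 or more of 58, while 35 or more gives 7.4% and 88.7%.
2. Then add one non-binding futility look, without pausing accrual, when the first 29 women treated at the phase II dose have a known clinical-benefit status. Consider closing if 14 or fewer have benefit.
3. Define the 29: include phase I women treated at that dose, and count women who stop before two cycles as without benefit. State how this fits with the two-cycle evaluability rule at the final analysis, because the figures assume the same counting at both points.
4. State the stopping probabilities (71%, 50%, 13.6% and 2.8% at true rates of 45%, 50%, 60% and 67%) and the error rates with the look: 82.2% power and 4.3% type I error at cut-off 36, or 87.9% and 7.2% at cut-off 35.
5. Give the expected accrual rate and the scan at which six months of stable disease is established, so that the likely saving can be judged.

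Cost: a short paragraph, one tally that has to allow for the scan review in section 6.1 and response confirmation in section 9.7.1, under one point of power, and a wider interval (about ±18 rather than ±13 points) if the trial closes near 29 women.

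### The phase II acceptance rule (35 or more of 58) has a 7.4% type I error, not the stated 4.3%; the stated error rates belong to 36 or more of 58

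*Combined protocol and SAP*

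**What the plan says.** Everything needed is in Section 16.2 (Sample Size Justification). The null is a clinical benefit rate of 50% or less. For the alternative, "the alternative hypothesis is that the clinical benefit rate of 67% or more is of considerable interest". The design has no interim look: "the sample size was calculated according to a single-stage design". On size, "The study will accrue a total of 58 patients". The decision rule is that "the combination therapy will be accepted if there are at least 35 responders out of 58 patients".

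The operating characteristics follow directly: "The design will have a 4.3% (< 5%) type-I error (false positive) rate". The plan puts power at 82.7%, above its 80% requirement, with the complementary 17.3% as the type II error.

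Section 16.1 confirms that the phase II part is single-arm and single-stage. Sections 16.3 and 16.4 give no other cut-off, test or confidence interval for clinical benefit, so this sentence is the only decision criterion for the phase II primary endpoint.

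**The concern.** In a single-stage design, the sample size, the cut-off and the two assumed rates fix the type I error and the power completely. A reader can therefore check whether the stated rule has the stated error rates. It does not: the false-positive rate comes out above 5% and the power above the stated value. Both move in the direction expected if the cut-off is one responder too low.

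What is at stake is the go decision. If exactly 35 of 58 patients benefit, the written rule accepts the combination, while the design that has the stated error rates would not. The plan offers nothing else to settle the matter, and a correction made after the count is known would look driven by the result.

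**Working it through.** **Inputs, all from Section 16.2:** n = 58; null rate p0 = 0.50; target rate p1 = 0.67; single stage; accept if the number of responders X is at least r, with r = 35 as written.

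**Formula.** For X binomial(n, p):

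P(X ≥ r) = Σ (k = r to n) C(n, k) p^k (1 − p)^(n − k)

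Type I error is this tail at p0; power is this tail at p1.

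**Which cut-off reproduces the stated figures (n = 58)?**

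| Accept if X is at least | Type I error (p = 0.50) | Power (p = 0.67) | Type II error |
|---|---|---|---|
| 34 | 0.1185 | 0.9307 | 0.0693 |
| **35 (as written)** | **0.0740** | **0.8871** | **0.1129** |
| **36** | **0.0435** | **0.8265** | **0.1735** |
| 37 | 0.0240 | 0.7478 | 0.2522 |
| Stated in the plan | 0.043 | 0.827 | 0.173 |

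The stated figures are those of the row for 36, to within 0.1 percentage point. The written rule misses the type I error by 7.4 − 4.3 = 3.1 points and the power by 88.7 − 82.7 = 6.0 points.

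**Hand check with the continuity-corrected normal approximation.** Under the null the mean is 58 × 0.50 = 29 and the SD is √(58 × 0.25) = 3.808. Under the target the mean is 58 × 0.67 = 38.86 and the SD is √(58 × 0.67 × 0.33) = 3.581.

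- r = 35: z = (34.5 − 29)/3.808 = 1.44, tail 7.4%; z = (34.5 − 38.86)/3.581 = −1.22, power 88.8%.
- r = 36: z = (35.5 − 29)/3.808 = 1.71, tail 4.4%; z = (35.5 − 38.86)/3.581 = −0.94, power 82.6%.

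**Other readings that might rescue 35:**

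- Normal approximation without continuity correction: 5.8% and 85.9%. Neither matches, and the first still exceeds 5%.
- Target of 2/3 instead of 0.67: power 87.6%. The type I error does not depend on the target and stays at 7.4%.
- Two-sided reading, doubling the tail: 2 × 7.40% = 14.8%.
- Denominator of 64, the ceiling on evaluable patients in Section 16.2: 35 or more of 64 has a type I error of 26.6%.

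**Where the two cut-offs disagree.** Only at X = 35:

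- P(X = 35) under the null: 0.0740 − 0.0435 = 0.0305, or 3.1%.
- P(X = 35) under the target: 0.8871 − 0.8265 = 0.0606, or 6.1%.

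At 35/58 = 60.3% the exact one-sided p-value is 0.074, and the lower limit of the exact 90% confidence interval is 48.7%, below the null value. At 36/58 = 62.1% the p-value is 0.043 and the lower limit is 50.4%. The plan specifies no interval; these limits are added only to show on which side of 50% each result falls.

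**The case against.** No alternative reading of the section makes 35 consistent with the stated error rates. Four weaker points deserve an answer.

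- *The match to 36 is not exact to the printed decimal.* This is correct. Exact power is 82.648% and exact type II error 17.352%, which round to 82.6% and 17.4%, against the printed 82.7% and 17.3%. Truncating the type II error to 17.3% and taking the complement would explain it. The residue is about 0.05 point, beside a 6-point gap for the written rule. It affects what the corrected text should print, not the finding.
- *The cause is inferred.* Also correct. A boundary meant as more than 35 but written as at least 35 is the natural explanation, because 35 is the largest count that does not reject the null at 5%. The documents do not confirm this. The contradiction between rule and error rates stands whatever its origin.
- *The cut-off appears once, so it could be a misread digit.* Nothing in that sentence looks damaged. A glance at the source page would settle it.
- *The practical reach is narrow.* The cut-offs differ at a single outcome, in a trial that decides only whether to study the combination further. That is fair as to probability. But the outcome lies on the decision boundary, and there the rule and its stated error rates give opposite answers.

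**Conclusion.** The concern holds. As written, the rule has a type I error of 7.4% against a stated 4.3% (7.4/4.3, about 1.7 times) and exceeds the plan's own 5% limit. Its power is 88.7% against a stated 82.7%. The stated figures belong to 36 or more of 58.

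This rests on the values in Section 16.2 (n = 58, 50%, 67%, single stage), on independent patients, and on the rule being applied to exactly 58 patients. It needs no outside figure. Because this is the only phase II decision rule, it must be corrected before the responder count is known. The sample size is sound: 58 patients with a cut-off of 36 meet both the below-5% and the above-80% requirement.

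**What to change.** In Section 16.2, require at least 36 responders out of 58 (equivalently, more than 35). Keep n = 58 and the 4.3% type I error. Print power as 82.6% and type II error as 17.4%, or note that 82.7% and 17.3% reflect rounding.

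The only other consistent repair is to keep 35 and restate the type I error as 7.4% and the power as 88.7%. That would mean withdrawing the claim of an error below 5%, so it is the less natural choice.

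The first repair changes one number and tidies two decimals. It adds no patients or assessments and raises the bar by one responder. Power falls by 6.1 points from what the written rule actually delivers (88.7% to 82.6%), which is essentially the level the plan already claims.

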7.1 General Considerations

Treatment will be administered on an outpatient basis. Patients will be instructed to start study drugs on Day 1 of each 28-day treatment period. One cycle is defined as 28 days of treatment. Prior to starting a cycle, all patients must continue to meet all inclusion criteria (see Section 5.1). No investigational or commercial agents or therapies other than those described below may be administered with the intent to treat the patient's malignancy. Patients will receive treatment until it is no longer of benefit to them. Patients may discontinue therapy at any time for any reason.

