7.4 Phase I Dose Modifications or Escalations

7.4.1 Phase I Component

For the Phase I dose escalation portion of the trial, patients will be enrolled in two cohorts (Level 0 and 1) with the following dose escalation rules:

Dose Level 0

The first three patients will start at Level 0:

- If 0 patients experience dose-limiting toxicity (DLT) during cycle 1, the dose will be escalated to Level 1.
- If 1 of the first 3 patients experience DLT in cycle 1, we will expand the cohort and 3 more patients will be treated at Level 0 for a total of 6 patients.

Phase I/II Trial of Letrozole and Sorafenib as First-Line Therapy in Postmenopausal Women with Hormone Receptor-Positive Locally Advanced or Metastatic Breast Cancer PI:

 If 1 of these 6 patients experiences DLT in cycle 1, the dose will be escalated to Level 1.

If 2 or more of the patients in this cohort experience DLT in cycle 1, we will have
exceeded the maximum tolerated dose (MTD) and will de-escalate to Level -1 and
enroll 3 patients. If no patients experience DLT during cycle 1, this will be the
recommended phase II dose.

Dose Level 1

The second cohort of three patients will be started according to the rules above and enrolled as follows:

- If 0 patients experience DLT at Level 1 in cycle 1, this will be our recommended phase II dose.
- If 1 of the first 3 patients experience DLT in cycle 1, we will expand the cohort and 3 more patients will be treated at Level 1 for a total of 6 patients.
- If 1 of these 6 patients experiences DLT in cycle 1, this will be our recommended phase II dose.
- If 2 or more of the patients in this cohort experience DLT in cycle 1, we will have exceeded the MTD and Level 0 will be the recommended phase II dose.

Each of the two dose levels of sorafenib will be given with letrozole at 2.5 mg orally daily as outlined in the dose escalation schedule listed in the following table:

Does Escalation Schedule				
Dose Level	Dose of Sorafenib			
Level 1	400 mg po twice a day			
Level 0	400 mg po daily			
Level -1	400 mg po every other day			

Intrapatient dose escalation will be allowed for patients enrolled at Level 0 and if they do not experience DLT during Cycle 1, they can escalate to Level 1 for Cycle 2.

DLT will be evaluated in the first cycle of therapy and defined as: Grade 3 or 4 non-hematologic toxicity (except alopecia, nausea, emesis that resolves to ≤ Grade 1 with symptomatic treatment) or Grade 4 hematologic toxicity that is thought to be related to sorafenib.

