7.5.2 Sorafenib Dose Modifications

Sorafenib specific modifications are outlined in the following tables:

Phase I/II Trial of Letrozole	and Sorafenib	as First-Line Therapy in Postmenopausal
Women with Hormone Receptor-	Positive Locally Advanced	or Metastatic Breast Cancer
PI:		

Table 7.5.2.1 Dose Modifications for Sorafenib for Hand-Foot Skin Reaction

Skin Toxicity Grade	Occurrence	Suggested Dose Modification
Grade 1: Numbness, dysethesia, paresthesia, tingling, painless swelling, erythema or discomfort of the hands or feet which does not disrupt the patients normal activity	Any occurrence	Institute supportive measures immediately and continue sorafenib treatment
Grade 2: Painful erythema and swelling of the hands or feet and/or discomfort affecting the patient's normal activities	1 st occurrence	Institute supportive measures and consider a decrease of sorafenib by 1 dose level. • If toxicity returns to grade 0–1 after dose reduction, increase sorafenib to full dose (per original dosing schedule) after 28 days • If toxicity does not return to grade 0-1 despite dose reduction, interrupt sorafenib treatment for a minimum of 7 days, until toxicity has resolved to grade 0–1 When resuming treatment after dose interruption, resume sorafenib at the next lower dose level for 28 days • If toxicity is maintained at grade 0–1 at reduced dose, increase sorafenib to full dose (per original dosing schedule) after 28 days
	2 nd or 3 rd occurrence	As for first occurrence, but upon resuming sorafenib treatment, decrease dose to the next lower dose level indefinitely Decision whether to discontinue sorafenib treatment should be made
Grade 3: Moist desquamation, ulceration, blistering or severe pain of the hands or feet, or severe discomfort that causes the patient to be unable to work or perform activities of daily	occurrence 1 st occurrence	Institute supportive measures and interrupt sorafenib treatment for a minimum of 7 days and until toxicity has resolved to grade 0–1 • When resuming treatment after dose interruption, resume sorafenib at the next lower dose level for 28 days • If toxicity is maintained at grade 0–1 at reduced dose, increase sorafenib to full dose (per original dosing schedule) after 28 days

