Anytime during treatment	Febrile episode (> 38.5°C) accompanied by ANC count < 1200/μL	Reduce 1 dose level for all subsequent cycles.
	A subsequent febrile neutropenic event	Discontinuation of protocol therapy

Table 7.5.2.3.A Dose Modification for Sorafenib Associated HematologicToxicity

Toxicity	Grade 1	Grade 2	Grade 3	Grade 4
Hematologic toxicities not listed above	Continue at the same dose level.	Continue at the same dose level.	Withhold dose until toxicity is grade ≤ 2 , then resume treatment at the same dose level. If patient experiences a second grade 3 toxicity, withhold dose until toxicity is grade ≤ 2 , then reduce dose to the next lower dose level and resume treatment.	Withhold dose until toxicity is grade ≤ 2, then reduce dose to the next lower dose level and resume treatment, or discontinue at the discretion of the principal investigator.

Phase I/II Trial of Letrozole	and Sorafenib	as First-Line Therapy in Postmenopausal
Women with Hormone Receptor-Pos	ifive Locally Advanced	or Metastatic Breast Cancer
PI:		

Table 7.5.2.4 Management of Treatment Emergent Hypertension

Grade	Management/Next Dose
Grade 1	Consider increased BP monitoring
Grade 2 asymptomatic and diastolic BP < 110 mm Hg	Begin anti-hypertensive therapy and continue agent.
Grade 2 symptomatic and/or persistant OR Diastolic BP ≥ 110 mm Hg OR	Agent should be held until symptoms resolve and diastolic $BP \le 100 \text{ mm Hg}$; also treat patient with antihypertensives and when agent is restarted reduce by 1 dose level.
Grade 3	If diastolic BP is not controlled (\leq 100 mm Hg) on the rapy reduce another dose level.
Grade 4	Discontinue therapy.

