7.8 Adherence/Compliance

Patient compliance in daily self-administration of the oral tablets will be assessed at each clinic visit. Patients will be given a medication diary and instructed to fill out how many tablets (letrozole and sorafenib) were taken each day and the time of day the drug was taken. At the end of each cycle of treatment, the actual amount of unused drug will be compared to the anticipated amount of unused drug and the patient's medication diary.

8. Toxicity Monitoring and Adverse Event Reporting

All patients who receive one dose of protocol therapy will be evaluable for assessment of toxicity. Prior to each cycle the treating physician will fully assess the patient's condition with respect to possible treatment related toxicities. All adverse events, whether observed by the physician or reported by the patient, occurring during the active portion of therapy, or up to 30 days after the last dose of treatment will be graded by a numerical score according to the NCI's Common Terminology Criteria for Adverse Events (CTCAE), Version 3.0 (http://ctep.cancer.gov/reporting/ctc.html) and recorded in the patient's medical record.

Phase I/II Trial of Letrozole (and Sorafenib as First-Line Therapy in Post Women with Hormone Receptor-Positive Locally Advanced or Metastatic Breast Cancer	menop	ausa
PI:		

Adverse events will be recorded on electronic case report forms in accordance with a study-specific data capture plan.

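### Phase I evaluability sets no minimum cycle-1 sorafenib dose, so a woman cut or held for a non-DLT toxicity can be scored as DLT-free at her assigned level

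*Combined protocol and SAP*

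**What the plan says.** - **Evaluability (16.2).** "Evaluable patients for the phase I portion are defined as study-eligible patients who have received at least one cycle of treatment". Section 7.1 adds: "One cycle is defined as 28 days of treatment". Neither names a dose.
- **DLT (7.4.1).** "DLT will be evaluated in the first cycle of therapy and defined as: Grade 3 or 4 non-hematologic toxicity", with exceptions for alopecia and for nausea and emesis that settle with treatment, "or Grade 4 hematologic toxicity that is thought to be related to sorafenib". A dose cut, a hold or a total of missed doses is not a DLT.
- **Decision rule (7.4.1).** Level 1 becomes the recommended phase II dose with 0 DLTs in 3 women, or 1 in 6 after expansion.
- **Cuts and holds.** For a first Grade 2 hand-foot reaction, Table 7.5.2.1 says: "Institute supportive measures and consider a decrease of sorafenib by 1 dose level". If the reaction does not settle on the lower dose, it says to "interrupt sorafenib treatment for a minimum of 7 days". For symptomatic or persistent Grade 2 hypertension, Table 7.5.2.4 holds sorafenib, then: "also treat patient with antihypertensives and when agent is restarted reduce by 1 dose level". Table 7.5.2.3.A withholds sorafenib for other Grade 3 hematologic toxicity, which is also not a DLT. All these tables stand under the Phase II heading of 7.5.
- **Supportive care (7.7).** Interruption or dose modification is allowed for skin toxicity, with no limit by phase. Rash and hand-foot reaction are described as usually Grade 1 or 2 and as appearing in the first six weeks.
- **Compliance (7.8).** "At the end of each cycle of treatment, the actual amount of unused drug will be compared to the anticipated amount of unused drug", and with the diary. No threshold is set and nothing links the count to evaluability.

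**The concern.** The recommended phase II dose is a primary objective (1.1.1) and fixes the sorafenib dose for phase II. The decision rests on three to six women per level. A level is meant to pass because women took that dose for a cycle without a DLT. As written, it can also pass because some of them were moved to a lower dose before a DLT could occur. If less drug means fewer DLTs, the error has one direction: the DLT count is too low for the assigned level, and the recommended dose can come out too high.

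The DLT window sharpens this. Table 7.5.2.1 returns a woman with a first Grade 2 hand-foot reaction to full dose after 28 days at the reduced dose. If that table applies in phase I, she clears the cycle-1 window on less than the assigned dose and goes back to it when a DLT no longer counts.

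**Working it through.** The plan states no operating characteristics for phase I, so there is no figure to reproduce.

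**1. Does any rule tie the DLT decision to the dose taken?** 16.2 asks for a cycle, 7.1 defines a cycle by days, 7.4.1 counts DLTs, and 7.8 measures intake without using it. The one same-dose condition, in 16.2, governs whether a phase I patient is pooled into phase II. No replacement rule is given. The answer is no.

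**2. How much drug might such a woman take?** Level 1 is 400 mg twice a day, so the cycle-1 total is 28 × 800 = 22,400 mg. A one-level cut goes to 400 mg a day.

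- Cut after day 7: (7 × 800 + 21 × 400) / 22,400 = 62.5%
- Cut after day 14: (14 × 800 + 14 × 400) / 22,400 = 75%
- Cut after day 21: (21 × 800 + 7 × 400) / 22,400 = 87.5%

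For a hold before the cut, which is the hypertension sequence, the table gives no duration. If it lasted 7 days from day 8 (an assumption), the share is (7 × 800 + 14 × 400) / 22,400 = 50%.

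**3. How often would a cohort contain one?** The share cut or held in cycle 1 is not in the documents. The chance of at least one among n women is 1 − (1 − share)^n.

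| Assumed share | 3 women | 6 women |
|---|---|---|
| 10% | 27.1% | 46.9% |
| 20% | 48.8% | 73.8% |
| 40% | 78.4% | 95.3% |

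**4. What does this do to the Level 1 decision, once Level 1 is reached?** From 7.4.1, with p the observed DLT probability:

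P(pass) = (1 − p)³ + 3p(1 − p)²(1 − p)³ = (1 − p)³ + 3p(1 − p)⁵

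Let r be the share reduced early, f the full-dose DLT rate and g the rate in reduced women. Under the current rule p = (1 − r)f + rg. All of r, f and g are assumptions. In the third row g = 0.15 × 0.15/0.40 = 0.05625, the same relative fall as in the first.

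| f, g | r = 0 | r = 20% | r = 30% |
|---|---|---|---|
| 40%, 15% | p = 0.40, pass 30.9% | p = 0.35, pass 39.6% | p = 0.325, pass 44.4% |
| 35%, 15% | p = 0.35, pass 39.6% | p = 0.31, pass 47.4% | p = 0.29, pass 51.5% |
| 15%, 5.625% | p = 0.15, pass 81.4% | p = 0.131, pass 85.0% | p = 0.122, pass 86.8% |

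**5. What would the repair do?** If reduced women without a DLT are replaced and those with a DLT are kept, the counted rate is p = [(1 − r)f + rg] / [(1 − r) + rg].

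- f = 40%, r = 20%: 0.35/0.83 = 0.422, pass 27.5%
- f = 40%, r = 30%: 0.325/0.745 = 0.436, pass 25.4%
- f = 35%, r = 20% and 30%: 0.31/0.83 = 0.373 and 0.29/0.745 = 0.389, pass 35.4% and 32.7%
- f = 15%, r = 20% and 30%: 0.13125/0.81125 = 0.162 and 0.121875/0.716875 = 0.170, pass 79.0% and 77.3%

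The repair errs on the low side, but in every case shown it lies nearer the r = 0 benchmark than the current rule does. At f = 40% and r = 20% it misses by 30.9 − 27.5 = 3.4 points, against 39.6 − 30.9 = 8.7.

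**The case against.** Several points limit the concern.

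- **The tables may not apply.** A reader might infer that phase I women will be reduced under the 7.5.2 tables. The documents do not establish this: the heading says Phase II, and 7.4 has no cut or hold rule. What stands in any phase is the skin-toxicity allowance in 7.7. Nothing forbids a cut in phase I, and if the tables do not apply there, cycle-1 modification has no rule at all.
- **The route is narrow.** Table 7.5.2.2 continues the same dose for general Grade 2 non-hematologic toxicity. The Grade 2 hand-foot cut is only to be considered, and a hold follows only if the cut fails.
- **The women did test the dose in part.** It is tempting to say they never took it. A woman cut after day 7 had a full week at Level 1 and 62.5% of the planned total. What she did not do is take it in full through cycle 1.
- **Holds may be excluded already.** A cycle of 28 treatment days could be read to leave out a woman with days off sorafenib. The plan does not say so, and letrozole may have continued. The point is firmest for a cut.
- **The rates are assumed.** Section 2.1.3.2 reports single-agent sorafenib at 400 mg twice daily as well tolerated, with one Grade 4 drug-related event in 54 patients. At a low DLT rate the effect is a few percentage points.
- **DLT under permitted modification is a defensible target,** since phase II uses the same tables. The plan does not adopt it, and 7.5.1 calls the phase II dose the maximum tolerated dose.
- **Replacing only DLT-free women tilts the other way** and could discard tolerability information. Both are true. The tilt is the smaller error in the cases computed, and reporting cuts and holds keeps the information.

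**Conclusion.** The gap is real in a limited form. Followed as written, 16.2 and 7.4.1 let a woman whose sorafenib is cut in cycle 1 for a non-DLT toxicity count as DLT-free at her assigned level; for a hold the text is ambiguous. The direction, a DLT rate biased down and a recommended dose that can be pushed up, follows if less drug means fewer DLTs. The size cannot be settled from the documents. With 20–30% reduced, it is about 9 to 13 percentage points on the chance that Level 1 passes at a 40% full-dose DLT rate, and about 4 to 5 points at 15%. The documents do not support saying that phase I women will be reduced under the Phase II tables, or that the chosen dose will be wrong. Because the result is a primary objective, rests on three to six women and can be protected cheaply, the plan should be changed.

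**What to change.** In 16.2, define a DLT-evaluable phase I patient as an eligible patient who either has a DLT in cycle 1, or takes at least a prespecified share of her assigned cycle-1 sorafenib without a DLT, measured from the 7.8 pill counts and diaries. The sponsor sets the share before the first dose decision. Replace women below it without a DLT for the dose decision and keep them in the safety analyses. At each level, report the number cut or held for toxicity beside the DLT count.

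Reconcile 7.4, 7.5.2 and 7.7 on whether the modification tables apply in phase I. Which rule is clinically right is for the sponsor to decide.

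The cost is wording, data already collected, and perhaps one or two replacement patients, who can count toward the 58 if treated at the recommended dose. There is also the slight conservative tilt: Level 1 passes 27.5% of the time against a 30.9% benchmark in the 40% example with 20% reduced.
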